6.1.4. MSC-NTF Benefit and Risk Assessment

ALS is a fatal neurological disease. There is currently only one product approved for the treatment of ALS, namely, riluzole, which was demonstrated to increase time to tracheostomy or death in patients randomized to riluzole compared to those randomized to placebo. No other products have been approved for the treatment of ALS since riluzole's approval in 1995. Thus, there remains a great unmet medical need for safe and more effective treatments for people with ALS.

Most of the current investigational therapies in development for ALS, such as anti-glutamatergic agents, drugs targeting protein misfolding and accumulation, antioxidant therapy and immunomodulatory agents, focus on one of multiple putative pathophysiologic mechanisms.

Cyto-therapy may hold the key to circumventing multiple hurdles in the ALS pathophysiological cascade (Morren JA et al. 2012). Apart from the replacement of lost or damaged motor neurons, stem cell implantation therapy may benefit ALS patients by an independent effect of cytoprotection.

Experimental data have shown that non-neuronal cell replacement can promote motor neuron survival and improved neuromuscular function (Corti S et al. 2010).

Preclinical studies in several animal models of neurodegenerative diseases have shown benefits of MSC-NTF transplantation, which support the evidence that these cells may be effective treatment of ALS patients.

Autologous MSC-NTF transplantation appears to be generally safe in the 28 ALS patients in whom the product has been administered in two open-label GCP compliant clinical trials as well as in five treatments in 4 patients with ALS in which the cells were administered on a "compassionate" basis treatment.

In the open-label studies we previously conducted, no serious treatment-related adverse events were reported in the 12 treated ALS patients who were administered the product via either IM or the IT route of administration or in the 12 patients that received a combined IT and IM administration of increasing doses of MSC-NTF cells (See section 6.1.2).

The dose for the proposed Phase 2 study is the highest IM and IT combined administration dose, found to be well tolerated in the Phase 2a clinical study and in the 'compassionate use' treated patients.

In our previous study a trend towards a decreased rate of decline on the ALSFRS-R and on FVC was observed in the IT treated patients over 6 months post-transplant as compared to the three months pre-transplant follow-up, suggesting that the product should be further evaluated in this indication.

MSC are plastic-adherent cells isolated from the mononuclear fraction of the bone marrow. The bone marrow compartment is a convenient source for MSC.

In summary, autologous transplantation of adult bone marrow-derived MSC offers practical advantages since:

- Bone marrow cells can be easily and safely obtained by needle aspiration. Although the crude bone marrow contains only very low numbers of MSC (1:10⁴-10⁵), they can be enriched and expanded *ex-vivo* from the bone marrow mononuclear cell fraction.
- There is no need for immunosuppression since rejection is not expected when autologous MSC are administered.

Potential risks of participation in this study are considered to be low, and include the following:

- Risks associated with bone marrow harvesting and related conscious sedation
- Risks of LP include post-LP headache and CSF leak that could potentially require treatment.
- Risks of IM administration may include local skin irritation at the injection sites.
- As this is an autologous treatment and there is variability between patients' cells' growth capabilities, there is also a possibility that patients' cells will not grow sufficiently and may not allow the required cell dose to be transplanted back.

Therefore, the potential benefits of IT and IM injections of MSC-NTFs justify the small risks associated with the harvesting of Bone Marrow and administration of this autologous product.

6.2. STUDY OBJECTIVES

6.2.1. Primary objective

To evaluate the safety of MSC-NTF transplantation via combined IT and IM injections in participants with ALS.

6.2.2. Secondary Objectives

To compare the change in slopes from the pre-transplantation period to the post-transplantation period in ALSFRS-R between the treatment and placebo groups through 12 and 24 weeks post-transplantation.

To compare the change in slopes from the pre-transplantation period to the post-transplantation period in SVC between the treatment and placebo groups through 12 and 24 weeks post-transplantation.

To compare the slope of the rate of decline in the ALSFRS-R at 12 and 24 weeks following transplantation relative to the 12-16 week baseline period before transplantation in all patients (both treatment and placebo groups).

To compare the slope of the rate of decline in SVC at 12 and 24 weeks following transplantation relative to the 12-16 week baseline period before transplantation in all patients (both treatment and placebo groups).

6.2.3. Exploratory Objectives

To compare the slopes of decline of hand-held dynamometry (HHD), and electrical impedance myography (EIM, for patients in whom this optional outcome measure is available) against placebo as well as during the 12-16 week pre-transplant monitoring period relative to the 24 week post-transplant follow-up period.

Determine feasibility of succeeding in blinding patients and caregivers to the treatment, in anticipation of a requirement to include the placebo group in the Phase III efficacy study.

To examine the CSF of ALS patients at baseline and two weeks after treatment for the presence of neurotrophic factors and possible ALS biomarkers.

6.3. INVESTIGATIONAL PLAN

6.3.1. Overall Study Design and Plan

This is the third clinical study of autologous MSC-NTF cells conducted by BrainStorm Cell Therapeutics and the first study conducted under this IND in the U.S. It is a Phase II randomized, double blind, placebo controlled multicenter study that will be conducted in 48 patients with early ALS (ALSFRS-R scores of ≥ 30) at up to 3 US study sites. After providing informed consent, each patient will undergo a 12-16 week baseline period during which monthly ALSFRS-R scores and SVCs will be obtained. During this period of time their bone-marrow will be harvested and deriving mesenchymal stromal cells will be expanded. Twelve to 16 weeks after screening, patients will undergo transplantation with their autologous MSC-NTF or matching placebo; product will be administered both intrathecally as well as intramuscularly as 24 IM injections given into the right biceps and triceps muscles, all at a single study visit. Following treatment they will have monthly visits at which the ASLFRS-R and SVC will be obtained, along with vital signs, laboratory tests and recording of concomitant medications and AEs.

All participants will undergo informed consent and sign a written informed consent document. Participants will be informed that in case their autologous bone marrow fails to grow adequate numbers of MSC they will not receive the transplant. All participants will be observed for a total of 12-16 weeks prior to undergoing a bone marrow aspiration

procedure to establish each individual's rate of progression over a total of about 3 months to be compared to post-treatment measures. This pre-treatment period also includes about four weeks of the cell propagation (see Figure 3).

The 48 participants will be randomized (3:1) into a treatment or into a placebo group which will occur at Visit 3. Cells from the treatment group participants will be propagated in a cell culture facility over a period that can range from 24 to 38 days. Participants in both the treatment and placebo groups will then undergo combined IT and intramuscular (IM) injections (Figure 1). Both groups will be monitored for 24 weeks post-treatment. Participants in each group will be monitored by evaluators blinded to the treatment group, using identical procedures during the pre-transplantation period and for an additional 24 weeks post-treatment. Participants will be followed by in-person visits and telephone visits at least monthly throughout the trial (see schedule of activities (SOA) in Tables 1 and 2).

The autologous production process is on a per-patient basis and begins upon fresh bone marrow aspirate arrival to the cleanroom facility and is completed once the cells are ready for transplantation. Because the production capacity of the cell manufacturing facility is limited, it will be the limiting factor for the rate of enrolment. Based on the production capacity limitations, patients are expected to be recruited at a rate of approximately 2-4 patients/months throughout the trial.

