Concomitant and Excluded Therapy	Study participants will be on a stable dose of riluzole for at least 30 days prior to screening or not taking riluzole at all, nor plan to begin riluzole during the study period.
SUBJECT POPULATION	
Number of Subjects Planned	48 total (3:1 randomization with 36 subjects in the active treatment arm and 12 in the placebo arm).
Major Inclusion Criteria	Age 18 to 75 years old. ALS symptom onset defined as first onset of weakness \leq 24 months and ALSFRS-R \geq 30 at the Screening Visit. Upright slow vital capacity (SVC) measure \geq 65% of predicted for gender, height, and age at the Screening Visit.
ASSESSMENTS	
Safety	Tabulation of AEs, changes in physical and neurological examination findings, hematology, serum chemistry, urinalysis, vital signs and requirement of concomitant medications.
Efficacy	The change in slope from the pre-transplantation period to the post-transplantation period in ALSFRS-R scores and slow vital capacity (SVC) through Weeks 12 and 24 post-transplantation for treatment compared to placebo. The change in slope from the pre-transplantation period to the post-transplantation period in ALSFRS-R scores and slow vital capacity (SVC) through Weeks 12 and 24 post-transplantation for each treatment group. The change in slope from the pre-transplantation period to the post-transplantation period in hand held dynamometry (HHD) and EIM (optional) through Weeks 12 and 24 post-transplantation for treatment compared to placebo. The change in slope from the pre-transplantation period to the post-transplantation period in hand held dynamometry (HHD) and EIM (optional) through Weeks 12 and 24 post-transplantation for each treatment group.
For the Schedule of Study Assessments, see Table 1 in Appendix 1.	

STATISTICAL METHODS AND ANALYSIS		

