6.5.3.3. Visit 3: Pre transplantation Visit (Week 8-10)

Visit 3 is the second visit of the pre-transplantation follow-up period (Week 8-10), about 1 week before Bone Marrow aspiration. Participants will undergo the following assessments:

- Review of concomitant medications
- Directed physical examination including weight
- Vital sign measurements
- Neurological examination
- Blood collection for hematology, coagulation and chemistry evaluations and a pregnancy test (Female participants)
- Blood collection for HBV (surface and core antigen), HCV, HIV 1 and 2 and HTLV I and II, Treponema pallidum, and CMV tests.
- Urinalysis
- SVC pulmonary function test
- Review of adverse events
- ALSFRS-R questionnaire
- Hand held dynamometry (HHD)
- Electrical impedance myography (EIM) will be collected only at centers that opt to participate in EIM data collection.
- Columbia Suicide Severity Rating Scale (C-SSRS) Since Last Visit

Following Visit 3, participants will be randomized into two arms at a 3:1 ratio: the treatment transplant arm (36) and the placebo transplant arm (12).

Any participant discontinuing the study prior to transplantation of cells (or placebo) injections will be replaced with another participant to meet the target of 48 transplanted participants.

Participants and medical team will be blinded to patient randomization.

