6.5.5. STUDY DISCONTINUATION

Subjects could choose to discontinue the study at any time, for any reason, specified or unspecified, and without prejudice. Participants could be discontinued from the study for any of the following reasons:

- Participants whose MSC fail to proliferate and to produce a sufficient amount of cells for transplantation (see section 6.3.1)
- At the participant's request
- At the discretion of the Investigator, if deemed appropriate, for any reason
- At the discretion of the Sponsor, if deemed appropriate, for any reason

In addition to the circumstances listed above for patients' withdrawal from the study, Brainstorm Cell Therapeutics Ltd. and the Investigators reserve the right to terminate the study at any time. In any case of early termination (ET) of the study, Brainstorm Cell Therapeutics Ltd. and the Investigators will ensure that adequate consideration is given to the protection of each subject's interest.

An ET visit will be conducted only for subjects who discontinue the study after treatment, post visit 5. The ET visit will include all the procedures required at end of study visit (Visit 10).

Any participant discontinuing the study prior to transplantation of cells (or placebo) injections will be replaced with another participant to meet the target of 48 transplanted participants.

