6.9.4.4. Determination of sample size

No formal sample size calculation has been performed. The sample size chosen was not based on statistical considerations. The total of 36 treatment and 12 placebo subjects are expected to be a sufficient number to obtain adequate characterization of common TEAEs and to observe trends for treatment effects on the efficacy measures chosen for this study.

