6.2 Full Analysis Set (FAS)

The FAS includes all randomized participants who were randomized.. The FAS will be analyzed based upon treatment group subjects were randomized to. Analysis on the FAS will be considered primary.

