7.2 Efficacy Endpoints

The efficacy endpoints are the following:

- Revised ALS Functional Rating Scale (ALSFRS-R)
- Slow Vital Capacity (SVC) (as a percent of normal)

[REDACTED]

[REDACTED]

[REDACTED]

[REDACTED]

[REDACTED]

[REDACTED]

8. General Considerations

Summaries for continuous variables will include the sample size, mean, standard deviation, median, minimum, and maximum. Minima and maxima will be reported with the same precision as the raw values; means, standard deviations, and medians will be presented to one additional decimal place than reported in the raw values. Summaries for discrete variables will include frequencies and percentages. All percentages will be rounded to one decimal place (i.e., XX.X%). Differences between treatment groups will be calculated as active – placebo and change from Baseline will be calculated as post-treatment – pre-treatment (OR follow-up visit – Baseline). The Baseline value will be defined as the last non-missing measure prior to initiation of investigational treatment. Additionally, for the pre-transplantation period and Transplantation Visits, change from screening summaries will be calculated as pre-transplantation period/Transplantation Visit minus screening.

All efficacy analyses will use one-sided alpha = 0.10 tests (which corresponds to a 2-sided alpha=0.20 test). The two-sided 80% lower confidence limit will be presented for which the lower bound is the 1-sided 90% confidence limit. In addition, the two-sided 90% and 95% confidence intervals around the difference between treatments as well as two-sided 95% confidence intervals around the point estimates within each treatment group will be provided. All summaries will be presented by treatment.

Statistical programming and analyses will be performed using SAS® Version 9.2 or higher.

[REDACTED]

[REDACTED]

[REDACTED]

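### Culture failure after randomisation can remove only active-arm patients, and the SAP's slope model, having no subject term, would keep their pre-transplantation slopes unmatched

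*Protocol*

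**What the plan says.** **Order of events.** Protocol 6.3.4 and SAP 3.2 place randomisation at Visit 3, one week before aspiration. All participants are aspirated, but Protocol 6.3.1 describes culture for one arm: "Cells from the treatment group participants will be propagated in a cell culture facility". SAP 3.3 says the same. Other text (the consent paragraph of 6.3.1, and 6.3.5) mentions culture without naming an arm, but nowhere says that placebo marrow is cultured.

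**What happens on failure.** Protocol 6.3.1: "Participants will be informed that in case their autologous bone marrow fails to grow adequate numbers of MSC they will not receive the transplant". Protocol 6.5.5 lists among the reasons for discontinuation: "Participants whose MSC fail to proliferate and to produce a sufficient amount of cells for transplantation". Protocol 6.5.3.3 adds: "Any participant discontinuing the study prior to transplantation of cells (or placebo) injections will be replaced with another participant". An early-termination visit is held only for those who stop after treatment (6.5.5).

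**Analysis.** Protocol 6.9.4.1 makes the treated-only mFAS primary. SAP 6.2 changes this to all randomised subjects, as randomised: "Analysis on the FAS will be considered primary". SAP 8.4 bases the main efficacy analyses on available data. SAP 10.2 fits a regression line to each subject's pre- and post-transplantation scores separately, with the post slope timed from the transplantation date. The slopes are then the response in a fixed-effects model with treatment, period and treatment by period. No subject term is listed, and the visible text has no rule for a subject who has only one of the two slopes.

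**The concern.** A placebo patient cannot fail the culture step as it is described, so this one route out of the trial depends on the assigned arm. It opens after randomisation, and replacement refills the transplanted total without restoring the patient who was lost.

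Calling the FAS primary suggests an intention-to-treat comparison. For an untransplanted active patient the change in slope cannot be formed. Under an available-data rule, however, the pre-transplantation slope from Visits 1 to 3 does exist, and nothing in SAP 10.2 keeps it out. The active arm's pre-period mean would then include patients who are absent from its post-period mean. The treatment-by-period term, which carries the between-arm efficacy comparison, would partly measure who was lost rather than what changed.

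**Working it through.** **1. The plan's own figure.** SAP 5 gives 95% probability of seeing an adverse event with a true rate of 8% among 36 active subjects. 1 − 0.92^36 = 0.9503, which agrees. It does not bear on the efficacy contrast. The sample size has no formula to reproduce ("No formal sample size calculation has been performed", Protocol 6.9.4.4), and no culture-failure rate is given in either document.

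**2. Which slopes exist.**

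| Patient | Pre slope | Post slope |
|---|---|---|
| Transplanted, either arm | Visits 1, 2, 3, 5 | Visit 5 onward |
| Active, culture failed | Visits 1, 2, 3 | none: no transplantation date, no planned assessments |

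**3. Inputs.** Planned allocation: "48 total (3:1 randomization with 36 subjects in the active treatment arm and 12 in the placebo arm" (Protocol synopsis). I assume that replacement brings the transplanted active arm to 36, each with both slopes. Protocol 6.3.7 quotes ALSFRS-R declines from 0.92 to 2.35 points/month; their difference is 1.43. These are two ends of a literature range and serve only as an illustrative extreme.

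**4. Formula.** Let m be the mean pre slope of the 36 transplanted active patients and u that of the k untransplanted ones.

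- Active pre mean = (36m + ku)/(36 + k) = m + [k/(36 + k)](u − m).
- Contrast = (active post − active pre) − (placebo post − placebo pre).
- Shift in contrast = [k/(36 + k)](m − u).

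**5. Numbers.**

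- k = 1, m = −0.92, u = −2.35: (1/37) × 1.43 = +0.039 points/month, an apparent benefit. This is 0.039/0.92 = 4% of the slower rate.
- k = 1 with the rates exchanged: −0.039, an apparent harm.
- k = 4, which is 4 of 40 or an assumed 10% failure rate: 0.10 × 1.43 = 0.143. This shows how the rule scales; it is not what the SAP reports.

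**6. Check by regression.** I set both slopes of all 36 active and 12 placebo subjects at −0.92, so that the true contrast is 0, and added k active subjects with only a pre slope of −2.35. Ordinary least squares on treatment, period and interaction gave 0.0386 for k = 1 and 0.143 for k = 4. With a fixed term for each subject, both became 0.

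**7. Likely k in this trial.** SAP 6.3 reports that the FAS and mFAS differed by one subject. Its mFAS required both treatment and at least 12 weeks of follow-up, so at most one randomised subject was untreated and k is 0 or 1. The subject may instead have been treated and left early; arm and reason are not given. SAP 16 says that the FAS definition was updated, so the definition behind the count is not certain.

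**8. Selection once pairs are required.** Suppose patients whose cells grow decline at a rate that differs by d from all active patients, and that treatment changes their slope by t. Their means are (μ + d) before and (μ + d + t) after, and the difference is t. The term d cancels.

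**The case against.** **Patients who stop are still followed.** A reader might infer that nothing is collected after a culture failure. Protocol 6.8.4.2 plans efforts to follow everyone who discontinues, with safety and clinical assessments. That stands. What is missing is narrower: ALSFRS-R and SVC are not named there, and no efficacy schedule applies.

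**Losses are not all one-sided.** Withdrawal, an investigator or sponsor decision, and the safety results required before aspiration (Protocol 6.5.3.4) can remove either arm, and replacement covers both. That also stands; only culture failure is tied to the active arm. The unpaired-slope problem is general, though. One unpaired placebo subject beside 12 would, on the same rates, move the contrast by (1/13) × 1.43 = 0.11 in the opposite direction, and the same pairing rule removes it.

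**Prognosis does not bias a change in slope.** It is tempting to say that any link between marrow growth and prognosis biases the result. Step 8 shows that it does not once pairs are used. Bias would need a link between growth and the pre-to-post change itself, and the documents give nothing from which to quantify one.

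**The effect is small and efficacy is exploratory.** Safety is the primary objective and the efficacy analyses look for trends. This limits the consequence but leaves the model as specified.

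**Multiple imputation is planned.** SAP 8.4 and 10.2 offer it as a robustness check, when warranted. It does not alter the main analysis, and the visible text gives no way to place scores for a subject with no transplantation date.

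**Conclusion.** The point holds as a specification fault in the SAP with a small expected effect. Randomisation before an arm-specific culture step, together with an all-randomised primary set and a second-step model without a subject term, lets an untransplanted active patient distort the change-in-slope contrast. The shift is k/(36+k) times the slope gap: 0.039 points/month for k = 1 on the illustrative rates, and zero if pairs are required. Its sign depends on whether the lost patient declined faster or slower than the others, and no document says which.

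This rests on 36 transplanted active patients with both slopes, on the visible model text being complete, and on SAP 10.2 being programmed as written. It does not show that the trial's efficacy result is materially biased: the SAP's own count puts k at 0 or 1. Nor is the FAS analysis simply a treated-only comparison. That is true of the post slopes, but the pre slopes of untreated subjects can still enter.

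**What to change.** **SAP 10.2.** Base the change-in-slope contrast on subjects with both a pre- and a post-transplantation slope. Either analyse each subject's post-minus-pre difference by treatment, or add a fixed subject term to the second-step model. (A random subject effect would still let an unpaired pre slope carry some weight.) State that the primary efficacy comparison is therefore effectively among transplanted subjects, although the population is named the FAS.

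**SAP 9.1.** Show the number randomised but not transplanted, with the reason, by arm. Most of this is already planned: 9.1 summarises FAS and Safety counts and reasons for discontinuation, and SAP 8 presents summaries by treatment. The change only makes the count explicit.

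**Cost.** SAP wording and a small programming change, with no new data. The standard error will change because the two slopes of a subject are now treated as a pair. The real downside is that untransplanted subjects leave the contrast, so it is not a full intention-to-treat estimate, and the SAP should say so.

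**Later studies.** Continued ALSFRS-R collection could be considered for untransplanted participants who agree; the telephone form is already used at Weeks 12 and 20. Two limits apply: a patient who learns that culture failed may infer active allocation, and a substitute for the transplantation date would have to be defined, since Protocol 6.5.3.5 allows 24 to 38 days from aspiration. The fix above does not depend on this.
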